6.1 The Paediatric Familial Hypercholesterolaemia Register (PFHR)

NHS HRA REC reference: 23/NE/0035

See full protocol in section 14 (APPENDIX: Full Protocol for NHS HRA REC reference: 23/NE/0035)

Existing Register size and representativeness: The PFHR was established in 2012 with the primary aim of monitoring LLT safety nationally, and feeding back to clinics on routine care.^{9,10} Up to and including 2019, there are 613 patients registered on the PFHR from across 39 clinical sites in England. Using a secure web-based portal, the Register captures routine clinical and demographic data from specialist clinics seeing patients with paediatric FH. Children treated with LLT and those without LLT treatment are both well-represented on the PFHR.¹⁰ Age, gender and lipid profiles are similar to those reported in other child FH populations,²⁶ and 75% are of white ethnicity (compared with 86% of the national UK population). The mean age of diagnosis is 9 years (Standard deviation (SD) 4) with a mean follow-up of 2.9 years (SD 1.8) and 57% initiating LLT at some point (mean age of initiation is 11 years, SD 3). The Register has been dormant since 2019 due to lack of funding.

6.1.1 **Protocol summary for re-instating the Register**

This study will reinstate the Register and collect up to 3.5 further years of follow-up data, by consenting new paediatric FH patients and collecting both retrospective and prospective clinical follow-up data using routinely recorded information from clinic appointments. **Clinical data collection will maintain collection of the original Register data items with the addition of data items on LLT adherence, reasons for non-adherence, and patient-reported side-effects/intolerance**. New patient registration across all clinics will be promoted with a focus on funding recruitment and data entry time from clinical case notes at key clinical sites. These sites are in areas based on larger concentration of case numbers, socioeconomically, ethnically, and geographically diverse populations, and underserved urban communities (Manchester, Bristol, Harefield, Wessex, Nottingham, all 5 sites in South Wales, London).

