Interviews will seek to understand the perceived acceptability, benefits, concerns or harms associated with starting LLT and how these may impact adherence, considering the variation in the ages participants started LLT. Interviews will also cover treatment and monitoring experiences and views on service provision and access, and how these could be improved. Questionnaires and interviews will inform information needs for patients and families.

Target recruitment is increasing the Register to 1,374 paediatric FH patients with clinical data entry, 500 participants for questionnaires and 40 participants for interviews. Clinical, questionnaire and interview consent forms and data collected will be securely stored at the University of Nottingham.

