6.2 The Clinical Practice Research Database (CPRD) paediatric FH cohort

CPRD RDG Protocol ID: 22-002278

The CPRD will be used as a secondary source of data to assess LLT treatment and potential sideeffects in children with FH, as well as medication adherence. This provides detailed longitudinal electronic health records from primary care with linkages to hospital admissions (but no access to specialist lipid clinic records). The general population in CPRD is highly representative of the sociodemographic distribution across the UK.¹¹ Our current unpublished research using CYP in the general population shows good national representation across socioeconomic and ethnic groups. Our June 2021 feasibility assessment of all CYP with diagnostic codes for FH in the CPRD GOLD database (which contains ~27% of the CPRD general population) showed they had a mean diagnosis age of 11 years, mean active follow-up 9 years, 64% were prescribed statins before age 18, and the mean number of LDL-C measures was 3, with almost half (42%) having prospective clinical records into adulthood. Using the whole of CPRD (GOLD and Aurum), we estimate at least 2,000 CYP with coded FH and another 1,600 with the clinical phenotype (based on our assessment of statin prescribing and hypercholesterolaemia coding). CPRD has reasonably complete information for these patients' gender, socioeconomic group, ethnicity, body mass index (BMI), however, it lacks the level of information on potential confounders that are available from the PFHR.

6.3 The Avon Longitudinal Study of Parents and Children (ALSPAC) cohort for deriving average cholesterol across childhood in the general (non-FH) population

ALSPAC Reference (B Number): B3815

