LDL-C changes in those exposed to LLT will be compared with changes in those never exposed or unexposed up to a certain age, measured as the difference between the earliest and later follow-ups. We will use inverse probability of treatment weighting techniques^{28,29} to balance exposed and unexposed groups according to both baseline and time-varying measured confounders: family history of CVD and/or FH in family, gender, genetic testing, body mass index (BMI), ethnicity, other health conditions, reasons for not being on LLT or non-adherence, process factors such as attendance frequency, and socioeconomic deprivation (using post-code linkage to index of multiple deprivation).

We will primarily estimate intention-to-treat effects, i.e. the effect of prescribing LLT to children with FH on LDL-C levels.³⁰ We will then estimate per-protocol effects, which corresponds to the effect of continuously taking LLT during the following period. Potential treatment non-adherence and loss to follow-up will be accounted for via censoring weights.³⁰ Missing data in both the LDL-C outcomes and confounders will be addressed using multiple imputation.

We will conduct sensitivity analyses to assess the extent to which the effects of age and LDL-C at initiation are robust to potential unmeasured confounding. We will adopt the E-value approach,³¹ which essentially explores how strong (association with both LLT initiation and LDL-C outcomes) the unmeasured confounders need to be to change the study conclusions. These analyses will be informed by discussions with clinical specialists and PPIE groups, and the HCP questionnaire.

This will be a descriptive analysis with the ultimate aim to derive effectiveness estimates that will feed into the cost-effectiveness model, where uncertainty will be fully propagated.³² However, initial assessment, based on pre- and post-puberty in current PFHR data shows children initiating LLT before age 12 years achieved a mean reduction in LDL-C of 2.199 after initial mean levels of 6.115 (pooled SD=2.51) and those initiating LLT at 12 or older achieved a mean reduction in LDL-C of 1.748 after initial mean levels of 5.570 (pooled SD=1.53). Demonstrating this difference at 90% power and 0.05 significance level with a 60-40 allocation ratio (as in the current Register) would require 560 children initiating LLT before age 12 and 376 initiating LLT at 12 or older, which is within our planned recruitment target.

Secondary analyses:

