This is descriptive research using the available paediatric patient population diagnosed with FH across the United Kingdom (except Scotland). Based on estimates of paediatric patients with FH currently being seen and newly presenting patients at clinical sites contacted by the Study Leads, we estimate at least 1,300 patients with clinical data entry on the PFHR over the next 5 years. Clinical sites will be contracted and funded for recruitment.

We estimate 400-500 participants with questionnaire data and 40 participants with interview data.

Page 24 of 37

Paediatric FH Register Study Protocol IRAS ID: 324246 18 June 2024 Final version 2.0

It is acknowledged that FH is currently underdiagnosed in the general population, however, cascade testing aims to increase earlier diagnosis. Based on currently available estimates from mid-2020²⁷, the general population age 0-19 years is 13,330,355 in England, 701,777 in Wales, and 484,495 in Northern Ireland. At an estimated paediatric FH prevalence of 0.28% in the UK,⁴ there are potentially 37,325 children living with FH in England, 1,964 in Wales, and 1,356 in Northern Ireland.

ADVERSE EVENTS

The occurrence of an adverse event as a result of participation in this study is not expected. There is no participation in any interventions as a result of participation in this study. Participation will have no consequences to an individual's clinical care.

ETHICAL AND REGULATORY ASPECTS

There are no interventions, separate clinical visits nor measurements required for participation in the study, beyond the patient's usual NHS clinical follow-up. Participation in the study involves consent for the patient's NHS clinical care information to be collected by the patient's clinical team for the study with the option for the patient or their parent/guardian to fill out questionnaires of self-reported information about their experience of FH, and the option of participating in an interview about their experience of FH.

Patients will be provided with contact details for the Study Management Team to discuss any concerns relating to participation and will be directed to discuss any personal clinical concerns with their FH clinical care team or general practitioner.

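### The power statement for Objective 1 sets a requirement of 936 treatment initiators against a target that counts all registrants; at the Register's own initiation rate about 783 are expected, with power of 84.5% to 87.7%

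*Protocol*

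**What the plan says.** Protocol section 7.1, Analysis (a), first calls the analysis descriptive and then gives a power calculation from existing Register data. Children starting LLT before age 12 had a mean LDL-C reduction of 2.199 mmol/L (SD 2.51). Those starting at 12 or older had 1.748 mmol/L (SD 1.53). The calculation is introduced with "Demonstrating this difference at 90% power and 0.05 significance level", uses a 60:40 split between the two age groups, and concludes that it "would require 560 children initiating LLT before age 12 and 376 initiating LLT at 12 or older, which is within our planned recruitment target".

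The target is in section 6.1.1: "Target recruitment is increasing the Register to 1,374 paediatric FH patients with clinical data entry". The sample size section of the appended Register protocol says "we estimate at least 1,300 patients with clinical data entry on the PFHR".

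Section 6.1 says that treated and untreated children are both well represented on the Register. It reports "57% initiating LLT at some point", at a mean follow-up of 2.9 years. The only other treatment rate is in section 6.2, for CPRD: "64% were prescribed statins before age 18".

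**The concern.** The requirement and the target count different things. The 560 and 376 are children who start LLT, whereas the 1,374 are all children on the Register, a large share of whom never start. A requirement for initiators can be called met only against a projected number of initiators, and the protocol gives none.

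Whether LDL-C reduction varies with age at initiation is part of Objective 1 and of the commissioned question. A reader of section 7.1 would conclude that the planned Register delivers 90% power for that contrast. If the number of initiators is lower, the stated power is too high, and nobody would be watching the count that determines it.

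**Working it through.** **Inputs.** From section 7.1: reductions 2.199 and 1.748, so d = 0.451 mmol/L; SDs 2.51 and 1.53; power 90%; alpha 0.05 (sidedness not stated; two-sided reproduces the figure); 60:40 split. From section 6.1.1: 1,374 registrants. From section 6.1: 57% initiation. From section 6.2: 64%. The SDs are taken as SDs of the reduction. The protocol labels each one pooled and does not say what was pooled.

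**1. Reproduce the protocol's figure.** (1.960 + 1.282)² = 10.507. Common SD = √[(2.51² + 1.53²)/2] = 2.079.
- Before 12: n = 10.507 × 2.079² × (1 + 1.5) / 0.451² = 558.
- At 12 or older: 558 / 1.5 = 372.

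This matches 560/376 closely (a t-based version gives 559/373), so the requirement itself stands: 560 + 376 = 936.

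**2. The requirement with the two stated SDs.**
- Before 12: n = 10.507 × (2.51² + 1.5 × 1.53²) / 0.451² = 507.
- At 12 or older: 338.
- Total: 845.

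**3. Initiators expected from 1,374.**
- At 57%: 0.57 × 1,374 = 783, which is 936 − 783 = 153 short of the stated requirement and 62 short of 845.
- At 64%: 0.64 × 1,374 = 879, which is 57 short of 936 but above 845.

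**4. Power for 0.451 mmol/L**, as Φ(d/SE − 1.960), and the difference detectable at 90%, as 3.242 × SE, both at 60:40:

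| Initiators | SD basis | SE | Power | Detectable at 90% |
|---|---|---|---|---|
| 783 (470/313) | common 2.079 | 0.1517 | 84.5% | 0.49 |
| 783 (470/313) | 2.51 and 1.53 | 0.1445 | 87.7% | 0.47 |
| 879 (527/352) | common 2.079 | 0.1431 | 88.4% | 0.46 |
| 879 (527/352) | 2.51 and 1.53 | 0.1364 | 91.1% | 0.44 |

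At the appendix figure of 1,300 registrants, 57% gives 741 initiators, with power of 82.5% (common SD) or 85.9% (two SDs).

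**5. Break-even initiation rate among 1,374.**
- Protocol's basis: 936 / 1,374 = 68.1%.
- Two stated SDs: 845 / 1,374 = 61.5%.

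**The case against.** The strongest reply is that 57% is not a final rate. It was seen at a mean follow-up of 2.9 years in children diagnosed at a mean age of 9. The plan adds retrospective data and up to 3.5 years of follow-up. Section 6.1.3 also gives priority to children aged 7 or older, on the ground that they can start LLT during the study. This stands: the rate may rise, and the documents do not exclude a rise to break-even. They do not project one either. Section 2.2 counts the existing 613 patients towards the total. If those stay at 57% (about 349 initiators), then (936 − 349)/761 = 77% of the new registrants must start for the protocol's 936, or (845 − 349)/761 = 65% for 845. The CPRD rate, at a mean follow-up of 9 years but for statins only, is 64%.

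A second reply is that the two stated SDs are the better basis and need only 845. This also stands, and on that basis the 64% scenario reaches 90%. It does not rescue the sentence, which claims that 936 is within target, and 783 is below 845 as well.

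A third reply is that the analysis is descriptive, and that its estimates feed an economic model in which uncertainty is propagated. That lowers the consequence. It does not make the feasibility statement right.

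**Conclusion.** The statement that 936 initiators fall within the recruitment target is not supported by the protocol's own figures. Unadjusted power for 0.451 mmol/L is 84.5% to 87.7% if 57% of 1,374 start LLT, and 88.4% to 91.1% if 64% do. The shortfall is moderate. It rests on those rates carrying over to the enlarged Register, on the 60:40 split, and on the stated SDs being SDs of the reduction. No confirmatory decision hangs on the test, so this is a moderate point.

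Three stronger readings are tempting, and the documents do not support them:
- **That 90% power cannot be reached.** It can, at 61.5% initiation with the two SDs or 68.1% on the protocol's basis.
- **That power is far lower once site clustering, weighting or adjustment for LDL-C at initiation is allowed for.** The calculation makes no such allowance, but the documents give no intraclass correlation, design effect or adjusted effect size. Any figure would be an invented input. Both age groups can occur within one site, so clustering need not inflate this contrast.
- **That the low end of the synopsis range makes the gap much larger.** The range is 1,000 to 2,000. At 57% that is 570 to 1,140 initiators, which straddles 936, so it settles nothing.

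**What to change.** In section 7.1, Analysis (a), replace the closing clause about the recruitment target with:
- the expected number of initiators, about 783 (57%) to 879 (64%) of 1,374;
- the resulting unadjusted power, about 84% to 88% at 57% and 88% to 91% at 64%, or the difference detectable at 90% power, 0.47 to 0.49 mmol/L at 57% and 0.44 to 0.46 at 64%;
- the basis for any higher initiation rate, if one is assumed;
- what the stated SDs measure, and which SD basis is used.

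In the quarterly site reports already described in the appended protocol, add the number of initiators with paired pre- and post-treatment LDL-C. Those reports already cover cholesterol measurements and LLT status, but not this count.

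The cost is one paragraph, one extra line in an existing report, and a somewhat less favourable stated power. No extra patients are needed.

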With around 1 in 250 children in the UK⁷ having the common heterozygote form, FH is as common as type-2 diabetes. However, over 80% of these individuals remain undiagnosed. To tackle this, the National Health Service (NHS) long term plan proposes to identify 25% of predicted FH individuals by 2024.⁸ This will lead to more CYP being diagnosed with the condition, hence the need for clear evidence-based guidance on when to initiate LLT.

5 Research questions (core study aim) and objectives 1 to 6

What is the clinical and cost-effectiveness of LLT in children with FH in the UK? How are these affected by the age of commencing treatment and different thresholds of serum LDL-C for treatment initiation?

To answer these questions the **objectives** are to:

1. Estimate **absolute and relative reductions in LDL-C, and in cumulative LDL-C, achieved in current practice with LLT**, and whether these vary by age and LDL-C at initiation of LLT

2. Estimate the incidence of side-effects and adverse events associated with LLT

3. Estimate LLT adherence at different ages and characterise reasons for variations in adherence

4. Understand the views of children and young people, their families and healthcare professionals, on information needs for starting LLT at different ages, and how these influence treatment acceptability, monitoring, and adherence

5. Estimate the impact of initiating LLT at different ages on the **costs of managing FH** over the short-term in children and young people

6. Estimate long-term health outcomes and NHS costs of starting LLT at different ages and LDL-C thresholds to identify a **cost-effective approach to management**

5.1 Study design and rationale:

Objectives will be met using a **mixed methods study design, building on existing established longitudinal cohort data sources:**

- **The Paediatric FH Register (PFHR)**^{9,10} (section 6.1 on page 11)
- Children with FH from the Clinical Practice Research Datalink (CPRD) general practice (GP) database¹¹ (section 6.2 on page 15)
- Children from the general (non-FH) population from the Avon Longitudinal Study of Parents and Children (ALSPAC)¹² (section 6.3 on page 15)

Further detail to characterise adherence and healthcare use will be obtained from **questionnaires sent to PFHR-registered patients**. Questionnaires will provide a framework for sampling **patients/families for qualitative interviews** that will further elucidate views, experiences, and information needs.

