Questionnaires sent to healthcare professionals (HCP) and qualitative interviews (section 6.4 on page 15) will also be used to describe adherence monitoring and healthcare use. Questionnaires will provide a framework for sampling HCPs for qualitative interviews that will further their elucidate views and experiences of working with the paediatric FH population, and their views on information needs for this patient group and their families.

We will estimate **long-term cost-effectiveness with a decision model parameterised by the above estimates**. **Systematic and pragmatic evidence reviews** will be conducted to address possible evidence gaps and provide alternative evidence sources for the economic model. Patient and public involvement and engagement (PPIE) will be incorporated via the study **Children and Young People's Advisory Group (CYPAG) and Parent and Carer Advisory Group (PCAG)**. These groups will be involved in co-development of the methodology and outputs at each stage of the research.

Risks and benefits of initiating treatment at different ages and LDL-C threshold levels are most efficiently and appropriately addressed by our mixed-methods study design, rather than a randomised controlled trial. NICE already recommend LLT initiation from age 10.⁴ A trial designed to observe the

effects of LLT initiation starting at various ages and LDL-C thresholds would be prohibitively resource intensive and require multiple arms and decades of follow-up to observe rare CVD outcomes (e.g., Of 203 CYP with FH treated in childhood re-contacted after 20-years, only one experienced a CVD event⁶). Furthermore, there are no robust surrogate outcomes that can be measured in childhood. Greater Carotid Intima-Media Thickness (CIMT) has been shown in children with FH compared with unaffected siblings¹³ and a small reduction in CIMT has been shown in short-term trials of statins,¹⁴ however, routine CIMT measurement is not currently recommended as its clinical prognostic utility, independent of LDL-C and other risk factors, is not yet established in FH nor in the general population.^{15,16}

Our study will yield a more nationally representative sample of CYP diagnosed with FH than previously available, to best inform future implementation of our findings across the country. Robust non-trial evidence (including mendelian randomisation studies) shows that reducing LDL-C earlier in life and maintaining optimal levels is an effective strategy to prevent CVD.¹⁷

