As well as assessing LDL-C reduction in current practice with LLT, we will estimate the reduction in cumulative LDL-C across childhood and adolescence. Accruing evidence indicates that cumulative exposure to LDL-C during adulthood increases later CVD risk despite an individual's current (adult) LDL-C level.¹⁷ A recent study of 4 pooled US cohorts replicated these findings when considering LDL-C exposure from early adulthood.¹⁸ Furthermore, paediatric FH specialists involved in the PFHR have highlighted that "normal" age-specific LDL-C levels in CYP are not known. Our established PPIE group raised concerns about how low LDL-C can be safely reduced, given that cholesterol is important for growth and neurodevelopment. NICE guidelines do not provide treatment targets for CYP due to a lack of evidence, however, recommended targets based on clinical consensus are available from the UK's cholesterol charity, the Hyperlipidaemia Education & Atherosclerosis Research Trust UK (HEART UK)⁵ and the European Atherosclerosis Society.¹⁵ Our study will explore the achievement of age-specific LDL-C levels after LLT initiation ("treatment targets") based on (i) recommended targets of 30-50% reduction or <3.5mmol/l,^{5,15} and (ii) population-expected levels at different ages across childhood/adolescence in the general (non-FH) population, the latter estimated using the ALSPAC cohort.¹²

Short term trials (up to 2 years) have shown **side-effects of LLTs** in children are rare² and early data from the PFHR showed no evidence of statin toxicity.¹⁰ We will use data from the PFHR, the CPRD and evidence reviews to characterise longer-term safety and growth in CYP with FH.

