The ALSPAC cohort will provide data for estimating average levels of LDL-C across childhood in the general (non-FH) population, a critical gap identified by clinical specialists and the NICE guidelines⁴ that needs addressing to inform FH treatment initiation and effective and safe target levels to which LDL-C should be reduced in CYP. ALSPAC is a longstanding cohort of children born in Avon in 1991-2 with repeated health and lifestyle measures into adulthood.¹² It is internationally unique in having repeated cholesterol and growth measures from birth to early adulthood. Cholesterol, growth and puberty measures are available at age 8,16,18 and 25 years (~7,000 CYP and ~2,000 with additional cholesterol near birth) as well as socioeconomic measurements, ethnicity and lifestyle factors that may be potential confounders. There are currently no other general-population British paediatric cohorts with such longitudinal measures.

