2. **CPRD** data on hospital admissions or general practice attendance will be used to assess sideeffects and adverse events. We will use post-marketing side-effects reported for each LLT type (e.g., headache, dizziness, unusual weakness, sleep problems). CPRD will provide a large sample to assess adverse events (e.g., rhabdomyolysis) as these will be extremely rare according to current evidence in adults.³⁵ Safety across childhood and into early adulthood will be assessed (with 42% of children with FH having CPRD records into adulthood).

3. Potential gaps will be addressed by the **systematic and pragmatic reviews**, as described in objective 1, that will include short and longer-term rare or serious side-effects of LLT including ezetimibe.

Analysis: Among children on LLT, liver enzyme (transaminases) measures >2.5 times the upper limit of normal before and after puberty will be described according to LLT type (of statin and more rarely used medications such as ezetimibe) and dose. Logistic regression models will be used to adjust for clinical and sociodemographic factors.

Age at first menstruation, weight-for-age and weight-for-height z-scores (BMI in adolescents) according to LLT exposure (type, dose, age at initiation) will be modelled using generalized estimating equations/growth models adjusting for clinical and sociodemographic factors.

Incidence rates of side-effects and adverse events will be described according to LLT exposure (type, dose, age at initiation) and Poisson regression will be used to adjust for clinical and sociodemographic factors.

Outputs

- Incidence of side-effects and adverse events
- Effects of LLT on growth and development
- Parameters for economic model (Objective 6): LLT adverse event rates

7.3 Objective 3: Estimate LLT adherence at different ages and characterise reasons for variations in adherence

Methods: We will measure adherence and characteristics related to variation in adherence using:

(a) Adherence captured at **routine follow-up visits recorded in the PFHR.** Based on discussions with our clinical specialist collaborators and Nottingham CYPAG and our PPIE group, these items will indicate recent adherence and reasons for sub-optimal adherence.³⁶

(b) **Patient questionnaires at baseline, 8, 16, 24 months** to obtain changes in adherence over time incorporating the Medication Adherence Report Scale.²⁷ The study CYPAG and PCAG will support interpretation of the questionnaire results.

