What are the health benefits and risks in the short-term and longer-term to monitoring health and starting treatment (mainly cholesterol-reducing medications, also known as LLT) at different ages and cholesterol concentrations during childhood and adolescence among people diagnosed with familial hypercholesterolaemia (also called clinical effectiveness)?

Page 11 of 37

Paediatric FH Register Study Protocol IRAS ID: 324246 18 June 2024 Final version 2.0

SECONDARY OBJECTIVE

Secondary objectives are to answer the following questions:

- For children and young people diagnosed with familial hypercholesterolaemia and their families, what is the acceptability of monitoring health and starting treatment (mainly cholesterol-reducing medications) in childhood and adolescence?
- How does following health monitoring and taking treatment medications as directed by health services (also called adherence) vary across childhood and adolescence and what are the short-term and longer-term health benefits and risks related to variation?
- How do health service costs of clinical familial hypercholesterolaemia monitoring and treatment in childhood and adolescence balance with the savings produced by preventing early heart disease in longer-term and does this provide value for money (also called cost-effectiveness)?

STUDY DESIGN

STUDY CONFIGURATION

The study comprises clinical data collection by healthcare professionals and patient-reported information obtained via questionnaire data collection and semi-structured interview data collection.

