Achievement of treatment LDL-C targets before and after puberty, and at age 18 will be estimated using logistic regression, assessing confounding. We will evaluate by age and LDL-C threshold at LLT initiation, the achievement of (i) recommended targets of 30-50% reduction or <3.5mmol/l^{2,22} and (ii) general (non-FH) population expected LDL-C concentrations from children in the Avon Longitudinal Study of Parents and Children (ALSPAC) who have repeated health and lifestyle measures into adulthood.²³

Incidence of side-effects and adverse events associated with LLT

We expect that the side effects related to LLT will be very rare in CYP with FH, so this will be a descriptive analysis presenting the side effects/adverse events.

Among children on LLT, liver enzyme (transaminases) measures >2.5 times the upper limit of normal before and after puberty will be described according to LLT type (of statin and more rarely used medications such as ezetimibe) and dose. Logistic regression models will be used to adjust for clinical and sociodemographic factors.

Age at first menstruation, weight-for-age and weight-for-height z-scores (BMI in adolescents) according to LLT exposure (type, dose, age at initiation) will be modelled using generalized estimating equations (GEE)/growth models adjusting for clinical and sociodemographic factors.

We will estimate the incidence of side effects/adverse events during follow-up calculated from the number of side effects/adverse events over the exposure period in person-years. Incidence rates of side-effects and adverse events will be described according to LLT exposure (type, dose, age at initiation) where numbers are sufficient. Poisson regression will be used to adjust for clinical and sociodemographic factors. We will test the model for overdispersion and use a negative binomial model as an alternative.

Treatment adherence and acceptability quantitative analysis

Adherence will be described quantitatively based on information captured in clinical data from routine follow-up visits. Acceptability and adherence will be described quantitatively based on participant characteristics in the questionnaire. High/low adherence will be described using the Medication Adherence Report Scale²⁴ according to children's age and other characteristics related to their FH and their/their parent/guardian beliefs about FH.

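### The protocol asks for the risks of starting LLT by age and by LDL-C level, but no stated safety or growth analysis includes LDL-C at initiation

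*Protocol*

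**What the plan says.** The appendix (Register protocol), under PRIMARY OBJECTIVE, asks: "What are the health benefits and risks in the short-term and longer-term to monitoring health and starting treatment", and completes the question with "at different ages and cholesterol concentrations during childhood and adolescence among people diagnosed with familial hypercholesterolaemia". Section 5.1 of the main protocol makes the matching claim: "Risks and benefits of initiating treatment at different ages and LDL-C threshold levels are most efficiently and appropriately addressed by our mixed-methods study design".

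The safety analyses are in section 7.2 and, in near-identical form, in the appendix under the heading on incidence of side-effects and adverse events:

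- Adverse events: "Incidence rates of side-effects and adverse events will be described according to LLT exposure (type, dose, age at initiation"). The appendix limits this breakdown to where numbers are sufficient.
- Age at first menstruation and weight z-scores: "according to LLT exposure (type, dose, age at initiation) will be modelled using generalized estimating equations (GEE)/growth models" (appendix wording).
- Raised liver enzymes: described before and after puberty, by LLT type and dose.

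All three are adjusted for clinical and sociodemographic factors that are not itemised.

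Two further passages bear on safety at low LDL-C. Section 5.1 reports that the patient and public group "raised concerns about how low LDL-C can be safely reduced, given that cholesterol is important for growth and neurodevelopment". Section 6.3 says that a gap in general-population LDL-C levels needs addressing "to inform FH treatment initiation and effective and safe target levels to which LDL-C should be reduced in CYP".

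**The concern.** The stated question has two axes for risk: age at initiation and LDL-C at initiation. The stated safety analyses carry only the first, and the liver-enzyme analysis carries neither. Both texts list the exposure factors explicitly, and the list does not match the objective. This is therefore more than model detail left to an analysis plan.

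At stake is the risk half of the comparison between LDL-C thresholds. The study would report how benefit varies with LDL-C at initiation, with no matching estimate for growth or adverse events. A reader could not tell whether risk is similar across starting levels or was simply not examined.

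**Working it through.** No sample size, power or error rate is involved, so the check sets the passages side by side.

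**Step 1. Factors listed for each outcome.**

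| Outcome | Where | Factors at initiation or of exposure | LDL-C at initiation named? |
|---|---|---|---|
| LDL-C reduction | 7.1 (a) and Outputs | age, LDL-C | yes |
| Cumulative and time-weighted LDL-C | 7.1 (b) | age, LDL-C | yes |
| Target achievement | 7.1 (c) | age, LDL-C threshold | yes |
| Adherence (Register, questionnaires) | 7.3 (a), (b) | age, LDL-C, among others | yes |
| Liver enzymes | 7.2, appendix | type, dose | no |
| Growth, age at first menstruation | 7.2, appendix | type, dose, age | no |
| Side-effect and adverse-event incidence | 7.2, appendix | type, dose, age | no |

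The CPRD prescription analysis in 7.3 (c) and the cost analysis in 7.5 also omit it, but their objectives are not posed by LDL-C. The risk question is.

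**Step 2. Does other text supply the estimate?**

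- Adjustment for unspecified clinical factors might include LDL-C, but the stated aim is adjustment. No estimate of risk by LDL-C is planned from it.
- Section 7.6 lets model inputs be conditioned on pre-treatment LDL-C if the data and the results of the other objectives allow. Objective 2 hands over adverse-event rates with no such breakdown.
- The ALSPAC models (7.1 (c)) describe LDL-C in children without FH. Target achievement is an efficacy outcome.
- The evidence reviews (7.1 (d), 7.2) state no breakdown by LDL-C.

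None fills the gap.

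**Step 3. Is the variable available?** The inclusion criteria (6.1.3 and appendix) prioritise, for treated cases, those with the treatment start date and the pre-treatment LDL-C. In CPRD it will be less complete: section 6.2 reports a mean of 3 LDL-C measures and no access to specialist lipid clinic records.

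**Step 4. What could be learned about rare events?** Suppose the existing Register's 57% ever treated carries over to the target of 1,374. Treated children = 0.57 × 1,374 = 783. The documents give no event risk, so take a range of 0.1% to 2% as an assumption:

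- 0.1%: 783 × 0.001 = 0.8 events, or 0.3 per third of starting LDL-C.
- 1%: 783 × 0.01 = 7.8 events, or 2.6 per third.
- 2%: 783 × 0.02 = 15.7 events, or 5.2 per third.

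The appendix suppresses counts below 5 in publications, so a table by thirds would mostly be blank. Growth is a continuous measure on most children and does not face this limit.

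**The case against.** The strongest reply is that section 7.2 matches its own numbered objective. Objective 2 asks only for the incidence of side-effects and adverse events; Objective 1 alone adds variation by age and LDL-C at initiation. The appendix also calls the safety analysis descriptive and expects side effects to be very rare. That is correct as far as it goes. It does not remove the mismatch, because the primary objective and section 5.1 both put risk and cholesterol level in the same question. The rarity argument stands for adverse events and liver enzymes, but not for growth.

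It could also be said that model terms belong in an analysis plan that is not shown. That would hold if the protocol left the factors open, but it lists them.

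Three stronger readings are tempting, and the documents do not support them:

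- *The primary question is how low LDL-C can safely go.* It is not. That is a patient-group concern in section 5.1 and part of the reason given for using ALSPAC in section 6.3.
- *Thresholds would be judged on efficacy alone.* They would not. Safety and growth are analysed by type, dose and age (liver enzymes by type and dose), and the economic model includes adverse events and long-term side-effects.
- *A harm confined to children with low achieved LDL-C would be diluted by a calculable amount.* Section 7.1 gives mean levels after LLT of 6.115 − 2.199 = 3.916 and 5.570 − 1.748 = 3.822 mmol/L, but no spread of achieved values and no cut-off for low. The planned analysis also splits by type and dose, so it does not average over all treated children.

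**Conclusion.** The mismatch is real and limited. The risk-by-LDL-C part of the stated primary question has no analysis: all three safety and growth analyses omit LDL-C at initiation, in both texts. The conclusion rests on reading the listed factors as the planned factors, and on adjustment not counting as estimation. It assumes nothing about whether risk does vary with starting LDL-C; the documents do not say. Its practical weight lies mainly in the growth outcomes.

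A smaller, separate point concerns section 6.3. LDL-C levels in children without FH show what is usual. They do not show what is safe to reach on treatment, so *safe* claims more than that source can give. A reader might infer that the study must therefore analyse achieved LDL-C as a main exposure. The stated objective does not require it: LDL-C at initiation is the minimum that answers the question asked.

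**What to change.** - In section 7.2 and the matching appendix section, extend the exposure to type, dose, age at initiation and LDL-C at initiation. Apply this to the growth models, and to the adverse-event and liver-enzyme models where numbers are sufficient. Because starting LDL-C may influence type and dose, report its estimate with and without those terms.
- Achieved on-treatment LDL-C may be added for growth only, labelled exploratory. It is a post-treatment variable shaped by adherence and dose changes, and growth may itself affect LDL-C, so its associations are open to confounding and reverse direction.
- If LDL-C at initiation is not added, narrow the risk wording in section 5.1 and in the appendix primary objective, with the synopsis to match.
- In section 6.3, qualify *safe* so that ALSPAC is described as giving usual levels in children without FH.

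The cost is one further term in models already planned, using a data item already prioritised in the Register. The price is wide intervals for rare events, which should be stated in advance. None of this sets or changes a treatment threshold.
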